5.2.4 Post-vaccination Reminders

Reminder calls or alerts are not intended to be an interview for collection of safety data. If the subject and/or parent(s)/legal guardian(s) wishes to describe safety information, this information should only be collected by a healthcare professional at the site, and the safety data described must be written down in the subject's medical chart.

Subject Diary Reminder Calls

Subject Diary reminder calls will be performed on Day 3 (all subjects) and Day 31 ("not previously vaccinated" subjects). The purpose of this call is to remind the subject and/or parent(s)/legal guardian(s)/ caregiver about completion of the Subject Diary. The call follows the Subject Diary Reminder Telephone Call Script provided to the site. The subject and/or parent(s)/legal guardian(s) should be reminded to contact the site via the telephone number provided in the informed consent to discuss medical questions.

5.3 Post-vaccination Visit(s)

Please refer to [Time and Events Table 3, 4, 5 and 6](#). Post-vaccination visits (clinic visit or safety phone call) will be performed on Days 22, 91, 181, or end of influenza season, whichever is longer ("previously vaccinated" subjects) or on Days 50, 120 and 209, or end of influenza season, whichever is longer ("not previously vaccinated" subjects). In the event that a scheduled or unscheduled visit or call/message coincides, procedures may be combined.

5.3.1 Post-vaccination Clinic Visit(s)

The following procedures will be performed on Day 22 for "previously vaccinated" subjects and on Day 50 for "not previously vaccinated" subjects:

1. At the clinic visit, the diary card will be reviewed. Please see section 3.4.2 for additional guidance on diary card review. Any AEs/Unsolicited AEs and concomitant medications reported on the diary cards should be reviewed by a trained health care professional.

If the diary card is not brought back, interview the subject or subject's parent(s)/legal guardian(s) to obtain information relating to unsolicited AEs including SAEs, medically attended AEs, AEs leading to study or vaccine withdrawal, NOCDs and

associated concomitant medications and all vaccinations ([see Section 6.5](#)). All safety information described by the subject or subject's parent(s)/legal guardian(s) must be written down in the source documents.

2. Perform a review of systems by interview that queries the subject or subject's parent(s)/legal guardian(s) as to any complaints the subject has experienced across each organ system.
3. Perform brief symptom-directed physical examination. The physical examination must be performed by the investigator or designee of the investigator, who is qualified to perform a physical examination in accordance with their institutional policy. Corresponding information is documented in the source documents and any relevant AE and/or NOCD findings noted during the physical examination are documented in both the source documents and electronic Case Report Forms (eCRFs).
4. Assess for influenza-like symptoms ([see Sections 5.3.3](#)).
5. Blood will be drawn (approximately 7 mL) from all subjects participating in the immunogenicity subset for serology testing. Details regarding the volume of blood and testing to be performed are in [Section 3.5](#).
6. Schedule safety telephone calls on Days 91 and 181, or end of influenza season whichever is longer, for "previously vaccinated" subjects and on Days 120 and 209, or end of influenza season whichever is longer, for "not previously vaccinated" subjects.

Remind the subject or subject's parent(s)/legal guardian(s) to contact the site if there are any questions and to contact the site immediately (or as soon as the subject is medically stable) if the subject has a medical condition that leads to a hospitalization, or a medically attended AE, or an emergency room visit.

5.3.2 Safety Follow-up Calls

Safety follow-up calls will be performed on Days 91 and 181, or end of influenza season whichever is longer ("previously vaccinated" subjects) or Days 120 and 209, or end of influenza season whichever is longer ("not previously vaccinated" subjects).

Safety follow-up calls are calls made to the subject by a blinded healthcare professional designated on the site log. These calls will follow a script which will facilitate the collection of relevant safety information. The subject/subject's parent(s)/legal guardian(s) will be interviewed according to the script. Safety follow-up calls performed on Days 91 and 181, or end of influenza season whichever is longer ("previously vaccinated" subjects) or Days 120 and 209, or end of influenza season whichever is longer ("not previously vaccinated" subjects) will collect information relating to a subset of unsolicited adverse events including SAEs, AEs leading to withdrawal, new onset of

chronic disease (NOCD), ILI and concomitant medications or vaccinations associated with those events. All safety information described by the subject must be written down in a designated location within the source document and not written on the script used for the telephone call.

The subject will be asked as to whether he or she was hospitalized or was evaluated at an emergency room for any illness since the site's last contact with the subject. If an SAE has been identified by the site staff during the interview which has not previously been reported by the subject, this SAE will be reported by the site within 24 hours to Seqirus or delegate. Any additional relevant medical history will be reported to Seqirus or delegate and recorded as needed.

ILI assessments will be performed to determine if symptoms of ILI are present. If the subject reports during phone contact that a medical event has occurred with symptoms consistent with an ILI, the subject will be asked to visit the site for further evaluation and potential NP swab taking. An NP swab for evaluation of the presence of influenza virus should be collected as soon as possible, preferably within 3 days, but up to 6 days following onset of protocol defined ILI symptoms (see [Section 5.4.1](#)).

The subject/subject's parent(s)/legal guardian(s) will receive a reminder of the next planned study activity, if applicable. The subject/subject's parent(s)/legal guardian(s) will be reminded to contact the site immediately (or as soon as the subject is medically stable) if the subject has a medical condition that leads to a hospitalization or an emergency room visit or to a visit to/by a doctor or is otherwise of concern.

The subject/subject's parent(s)/legal guardian(s) will be reminded to contact the site immediately if the subject experiences symptoms meeting primary protocol-defined ILI criteria to have a NP swab collected for evaluation of the presence of influenza virus (see [Section 5.4.1](#)).

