
enhance the understanding of immune responses to QIVc vaccination. This study is a regulatory requirement to support the licensure of QIVc for use in children ≥ 4 years of age in the United States (US). Children ≥ 2 years of age are enrolled in this study to further evaluate QIVc in a broader age range and to support submissions in various global regions.
 
The purpose of this study is to demonstrate the efficacy (absolute vaccine efficacy [aVE]), immunogenicity, and safety and tolerability of QIVc compared to non-influenza comparator vaccine in subjects ≥ 2 years to < 18 years of age. If there is more than one season, data from all seasons will be combined.
		

Efficacy Objectives:
 
Efficacy will be evaluated in all subjects in relation to cases occurring > 14 days after last vaccination and until the end of the influenza season.
 
Primary Efficacy Objective(s):
 
To demonstrate absolute vaccine efficacy of QIVc versus a non-influenza comparator determined by first occurrence RT-PCR or culture confirmed influenza, due to any influenza Type A and B strain in subjects ≥ 2 years to < 18 years of age.
 
In case of successful demonstration (see section 8.2) of the primary efficacy objective:
 
Co-Primary Efficacy Objective(s):
 
To demonstrate absolute vaccine efficacy of QIVc versus a non-influenza comparator determined by first occurrence RT-PCR or culture confirmed influenza, due to any influenza Type A and B strain in subjects ≥ 3 years to < 18 years of age.
		

Name of Sponsor: Seqirus UK Ltd	Protocol number: V130_12	Generic name of study vaccine(s): Cell-Based Quadrivalent Subunit Influenza Virus Vaccine (QIVc) Meningococcal (Groups A, C, Y, W-135) Conjugate Vaccine (Men ACWY)

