2.3 Exploratory Objective(s)

Exploratory Efficacy Objective:

The following objective will be evaluated in the age cohorts: ≥ 3 years to < 18 years of age, and ≥ 2 years to < 18 years of age:

To further characterize the efficacy of QIVc, with specific attention for all-cause mortality, all-cause pneumonia and all-cause otitis media.

Exploratory Immunogenicity Objective:

The following objective will be evaluated in a subset of subjects in the age cohorts: ≥ 3 years to < 9 years of age, and ≥ 2 years to < 9 years of age:

To further characterize the immune response, additional immunogenicity analyses may be conducted using other assays such as MN

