5.3.3 Active Influenza Surveillance Phone Calls

Active surveillance for ILI for each subject will be conducted weekly via telephone from Day 1 and until the end of the influenza season. The subject and/or subject's parent/legal guardian/ caregiver will be asked via phone a scripted set of questions to determine if symptoms of ILI are present. The purpose of the phone call is to trigger a clinic (or home) visit and a NP swab sample collection if ILI symptoms are present. Should ILI symptoms be present, the subject and/or subject's parent/legal guardian will also be reminded to complete the ILI booklet. Phone calls are not intended to collect any clinical data. Site personnel's follow up on all cases meeting primary protocol-defined ILI criteria is to be documented in the subject's source records and monitored in order to ensure that all subjects with ILI symptoms are scheduled for the NP swab sample collection visit as soon

as possible within 3 days, and up to 6 days following onset of protocol defined ILI symptoms.

The subject and/or subject's parent/legal guardian will also be reminded to contact the site immediately if he or she experiences symptoms meeting primary protocol-defined ILI criteria to have a NP swab collected for evaluation of the presence of influenza virus.

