5.4 Unscheduled Visits

5.4.1 Subjects Meeting the Influenza-Like-Illness Criteria

Clinic Visit or Home Visit – Obtaining NP Swab

Subjects will be asked to come to the site for an unscheduled clinic visit when experiencing symptoms meeting the primary protocol-defined ILI criteria. Subjects will be reminded to bring their ILI booklet. In the exceptional case that a clinic visit is not feasible, a home visit may be considered. The visit should occur as soon as possible, preferably within 3 days, and up to 6 days following onset of protocol defined ILI symptoms. During the visit the following procedures should be carried out:

- Assess ILI symptoms and assess associated medication. Document any anti-viral medication use from the first day of onset of ILI symptoms.
- Collect a NP swab for evaluation of the presence of influenza virus following the procedures for collecting, processing and shipping as described in the Lab Manual.
- Evaluate the subject's body temperature (preferably oral), heart rate, respiratory rate and blood pressure and perform a symptom-directed physical examination.
- Record the ILI, related information, medically-attended adverse events from ILI onset and associated concomitant medication in the source documents and in the eCRF (ILI-report and adverse events section).
- Schedule in next study activity and hand out new ILI booklet.

ILI Follow-up Safety Call

An ILI follow-up safety call will be performed at 30 (+7) days after primary protocol-defined ILI onset, amongst subjects who have had their NP swab obtained

During the visit the following procedures should be carried out:

- Assess ILI symptoms and associated medication, if any.
- Assess for medically-attended adverse event.
- Remind subject of next study activity.

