8.1.2 Secondary Endpoint(s)

8.1.2.1 Secondary Safety Endpoint(s)

Safety will be assessed by calculating:

- The percentage of subjects with solicited local and systemic adverse events for 7 days following vaccination at Day 1 (“previously vaccinated” subjects) or Day 1 and Day 29, (“not previously vaccinated” subjects) in the QIVc group and the non-influenza comparator vaccine group.
- The percentage of subjects with all unsolicited AEs will be assessed from Day 1 to Day 22 for “previously vaccinated” subjects or Day 1 to Day 50 for “not previously vaccinated” subjects in the QIVc group and in non-influenza comparator vaccine group.
- Percentage of subjects with SAEs, AEs leading to withdrawal from the study and NOCDs reported during the subject’s entire participation in the study, i.e. from Day 1 to Day 181 (for “previously vaccinated” subjects) or to Day 209 (for “not previously

vaccinated” subjects), or until the end of influenza season, whichever is longer, and all medications associated with these events.

- Percentage of subjects with medically-attended adverse events within 30 days after of first occurrence RT-PCR confirmed ILI.

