8.1.3.2 Exploratory Efficacy Endpoint(s)

The measures for exploring efficacy are as follows:

- Number of deaths as derived from SAE forms
- Number of subjects with pneumonia as derived from AE forms
- Number of subjects with physician-confirmed otitis media as derived from AE forms

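### After Day 22/50 the only scheduled query described for office-managed pneumonia or otitis media is triggered by an ILI, so these exploratory counts are not truly all-cause and their capture can differ by arm

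*Protocol*

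**What the plan says.** Protocol 2.3 aims to characterise efficacy "with specific attention for all-cause mortality, all-cause pneumonia and all-cause otitis media". Protocol 8.1.3.2 defines the two morbidity measures as "Number of subjects with pneumonia as derived from AE forms" and "Number of subjects with physician-confirmed otitis media as derived from AE forms". SAP 2.3.2 and 11.3 repeat them, and SAP 11.3 tabulates them by vaccine group on the Efficacy FAS. Neither document gives these counts an onset window, a dedicated question or a dedicated form.

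Collection of all unsolicited AEs is limited in time. Protocol 8.1.2.1 states: "The percentage of subjects with all unsolicited AEs will be assessed from Day 1 to Day 22", with Day 50 for two-dose subjects, and Protocol 3.4.1 gives the same limits. The row for assessing all AEs appears in the treatment-period schedules (Tables 3 and 5) and is absent from the follow-up schedules (Tables 4 and 6). Under Protocol 5.3.2, the Day 91/181 and Day 120/209 calls "will collect information relating to a subset of unsolicited adverse events including SAEs, AEs leading to withdrawal", new onset of chronic disease and ILI. On the weekly surveillance calls, Protocol 5.3.3 says: "Phone calls are not intended to collect any clinical data".

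An ILI opens a further route. Medically attended AEs are assessed at the ILI visit and again at a call 30 days after onset, the call being made "amongst subjects who have had their NP swab obtained" (Protocol 5.4.1). Protocol 3.8 sends such events to the AE eCRF.

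**The concern.** A child with otitis media or pneumonia treated in a doctor's office in mid-season reaches the AE form by one of two routes: the family volunteers it, or the child had an ILI and was therefore asked. The second route lies downstream of the vaccine's own effect. If QIVc prevents influenza, fewer QIVc children have an ILI, fewer are asked, and fewer otitis or pneumonia diagnoses are recorded, including those that influenza did not cause. A between-arm difference in the table could then be read as efficacy when part of it reflects who was questioned. Meanwhile, most of the days on which every child is asked about every AE come before the plan counts efficacy cases at all.

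**Working it through.** The plan states no coverage figure, so there is none to reproduce.

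**Inputs from the documents**
- Last dose on Day 1 or Day 29 (Protocol 3.1).
- Efficacy window: "cases occurring > 14 days after last vaccination and until the end of the influenza season" (Protocol Synopsis, Efficacy Objectives). It starts at 1 + 15 = Day 16, or 29 + 15 = Day 44.
- All-AE collection to Day 22 or Day 50; visit window −1 to +4 days (Tables 3 and 5).
- Follow-up to Day 181 or 209. Check: 181 − 1 = 180 and 209 − 29 = 180, matching Protocol 3.2.
- Northern Hemisphere season ends at the end of June (Protocol Definitions).
- Planning event rates: 8% comparator, 4% QIVc (Protocol 8.6).

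**Assumptions not in the documents**
- The general >14-day window applies to these counts.
- Last vaccination falls between 1 October and 1 March.
- Background non-influenza ILI is 10% to 40%, equal in both arms.

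**Share of the window after all-AE collection ends**
- One dose: 181 − 16 + 1 = 166 days, of which 22 − 16 + 1 = 7 are covered.
- Two doses: 209 − 44 + 1 = 166 days, of which 50 − 44 + 1 = 7 are covered.
- Not covered, either regimen: 159/166 = 95.8%.
- With the visit window (6 to 11 days covered): 160/166 = 96.4% down to 155/166 = 93.4%.
- To 30 June: 251/258 = 97.3% for 1 October, and 100/107 = 93.5% for 1 March. Adding the visit window widens this to 252/258 = 97.7% and 96/107 = 89.7%.
- Of the all-AE days, 15 of 22 (one dose) and 43 of 50 (two doses) precede the efficacy window.
- Over whole participation, the share after all-AE collection is 159/181 = 87.8% (one dose) and 159/209 = 76.1% (two doses).

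**Routes to an AE form after Day 22/50**

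| Route | Scheduled? | Needs an ILI? |
|---|---|---|
| SAEs at follow-up and termination calls (5.3.2, 5.5) | Yes | No |
| Hospital or emergency-room evaluation for any illness (5.3.2, 5.5) | Yes | No |
| Family contacts the site after a doctor visit (5.3.2, 7.1.2) | No | No |
| Medically attended AE after ILI (5.4.1) | Yes | Yes |

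A non-serious diagnosis made in a doctor's office falls only in the last two rows. The hospital and emergency-room question is also incomplete: Protocol 5.3.2 requires expedited reporting of an SAE it uncovers, but lets other history be recorded as needed, without requiring an AE form.

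**Size of the possible distortion**

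Let b be the background ILI percentage in each arm. The number of ILI-triggered queries is then proportional to b + 8 in the comparator arm and b + 4 in the QIVc arm. For an event unrelated to influenza and found only through that query, the apparent reduction is 1 − (b + 4)/(b + 8) = 4/(b + 8).

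| b | Calculation | Apparent reduction |
|---|---|---|
| 10 | 4/18 | 22% |
| 20 | 4/28 | 14% |
| 30 | 4/38 | 11% |
| 40 | 4/48 | 8% |

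If only a fraction s of the comparator events came solely through that query and the rest were captured equally in both arms, the reduction is s × 4/(b + 8). The tabled values are the upper bound at s = 1.

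**The case against.** A reader might infer that the efficacy period goes unqueried, or that all later capture depends on having an ILI. The documents do not support either. Protocol 5.3.2 and 5.5 ask every subject, regardless of ILI or arm, about hospitalisation or emergency-room evaluation for any illness, and SAEs are collected throughout. Families are told to contact the site after a doctor visit (5.3.2) and about medically attended events generally (7.1.2).

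Other text suggests that collection does not stop. Protocol 7.1 runs AE observation to Day 181/209 or the end of season. Protocol 7.1.2 has remaining unsolicited AEs gathered by interview and record review at the next visit, pointing to a section that includes the safety calls. Protocol 8.4.3.1.3 and SAP 13.3 tabulate AEs with onset on Day 23–181 and Day 51–209. The calls follow a script that is not among the documents, and the listed items are introduced as inclusions, so further questions are possible.

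The objective is also exploratory and descriptive. No vaccine efficacy estimate, interval or test is planned for pneumonia or otitis media.

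Much of this stands, and it limits the point to non-serious, office-managed events. It does not remove it. Spontaneous reporting is passive while the post-ILI query is active, so the asymmetry between children with and without an ILI remains. The passages that extend AE collection contradict Protocol 3.4.1, 5.3.2 and 8.1.2.1 and do not settle the question. Sites could follow either, and a Day 23–181 table could look complete when it is not.

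**Conclusion.** The point holds in limited form. About 96% of the efficacy window (roughly 90% to 98%) falls after scheduled all-AE collection, provided the general >14-day window applies; neither document says so for these counts. In that period, office-managed otitis media and pneumonia are systematically sought only after an ILI, as far as the documents describe. The resulting counts are not all-cause, and any imbalance in ascertainment is expected to favour QIVc.

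The 22% to 8% range is an upper bound resting on assumed background ILI rates and on capture through the ILI query alone. A reader might take it as the false efficacy the trial would report; the other capture routes and the absence of a planned efficacy estimate rule that out. Nor does it follow that the whole objective is unanswerable: all-cause mortality comes from SAE forms and is unaffected. The primary and co-primary analyses are not touched. This is a worthwhile, inexpensive improvement to an exploratory descriptive analysis.

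**What to change.** 1. Add scripted questions on physician-diagnosed otitis media and on pneumonia since last contact to the existing Day 91/181 and Day 120/209 calls for every subject. Require an AE form for any positive answer, whatever its seriousness or link to an ILI.
2. In SAP 11.3, tabulate events with onset more than 14 days after last vaccination to the end of the season.
3. Reconcile Protocol 3.4.1, 5.3.2 and 8.1.2.1 with Protocol 7.1, 7.1.2 and 8.4.3.1.3 and SAP 13.3, so that there is one stated collection period for unsolicited AEs.
4. If collection cannot change, label the pneumonia and otitis media counts by the routes that actually captured them, drop the all-cause efficacy description for those two, and show ILI-triggered events separately.

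The cost is two questions on calls already scheduled, a few more AE forms and a short SAP edit. The downside is recall over about 90 days (181 − 91 = 90; 209 − 120 = 89), longer when the last call moves to the end of the season: for a one-dose child vaccinated on 1 November, 30 June is Day 242, and 242 − 91 = 151 days.

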5.3.3 Active Influenza Surveillance Phone Calls

Active surveillance for ILI for each subject will be conducted weekly via telephone from Day 1 and until the end of the influenza season. The subject and/or subject's parent/legal guardian/ caregiver will be asked via phone a scripted set of questions to determine if symptoms of ILI are present. The purpose of the phone call is to trigger a clinic (or home) visit and a NP swab sample collection if ILI symptoms are present. Should ILI symptoms be present, the subject and/or subject's parent/legal guardian will also be reminded to complete the ILI booklet. Phone calls are not intended to collect any clinical data. Site personnel's follow up on all cases meeting primary protocol-defined ILI criteria is to be documented in the subject's source records and monitored in order to ensure that all subjects with ILI symptoms are scheduled for the NP swab sample collection visit as soon

as possible within 3 days, and up to 6 days following onset of protocol defined ILI symptoms.

The subject and/or subject's parent/legal guardian will also be reminded to contact the site immediately if he or she experiences symptoms meeting primary protocol-defined ILI criteria to have a NP swab collected for evaluation of the presence of influenza virus.

